## **16) Withdrawal of Subjects**

Subjects may be withdrawn without their consent if they acquire any medical issues during the study period which require the use of any other topical medications, oral or parenteral steroids, oral or parenteral antibiotics. They may also be withdrawn if they are found to have any abnormal sensitivity/allergy to the ALA.

If a subject is to be withdrawn without their consent, they will be contacted and the reason(s) for their withdrawal will be explained in full. No further data will be collected from the subject.

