### **15) Provisions to Monitor the Data to Ensure the Safety of Subjects**

PROTOCOL TITLE: Pilot study for the use of photodynamic therapy in the treatment of seborrheic dermatitis

The subjects will be monitored clinically during the treatment for any evidence of side effects such as pain or blisters. All of the treatments are done with topical ALA, which is an FDA approved drug.

No regular blood draws or labs will be necessary. No systemic effects are anticipated because all of the treatments are localized topical applications.

However, the patient will be given a contact number on the consent forms in case there are any treatment related adverse effects such as erythema, blisters, pain, or secondary infection. Any side effects will be noted in a secure document. Secondary infections will be treated with appropriate antibiotics and local inflammation will be treated with topical steroids as necessary.

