## **17) Risks to Subjects**

There is a low chance for any physical, psychological, social or legal injury from participation in the study. The patient will be warned of the standard risks of treatment with topical ALA including erythema, pain, blisters, increased temporary photosensitivity for 24 hours after treatments, and risk for hyper- and hypopigmentation.

These potential adverse events will be localized and can be adequately managed and controlled with wound care and topical antibiotics, if the subject were to develop a secondary infection at the treatment sites. It is also possible, although unlikely, that the subject may develop contact dermatitis after exposure to the topical ALA. This can be adequately managed with topical steroids and topical antibiotics, if necessary.

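### Section 16 stops all data collection after withdrawal without consent and makes no exception for side effects, although a reaction to ALA is itself a ground for withdrawal

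*Combined protocol and SAP*

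**What the plan says.** Section 16 (Withdrawal of Subjects) gives two grounds on which a subject may be withdrawn without consent. The first is a medical issue arising during the study "which require the use of any other topical medications, oral or parenteral steroids, oral or parenteral antibiotics". The second concerns the study drug: "They may also be withdrawn if they are found to have any abnormal sensitivity/allergy to the ALA". The subject is then contacted and told why, and the section closes with the rule "No further data will be collected from the subject". It states no exception.

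Section 15 (Provisions to Monitor the Data to Ensure the Safety of Subjects) describes safety monitoring: "The subjects will be monitored clinically during the treatment for any evidence of side effects such as pain or blisters". It gives subjects a contact number for treatment-related adverse effects and continues: "Any side effects will be noted in a secure document". That sentence is not limited to subjects still in the study. On treatment it says: "Secondary infections will be treated with appropriate antibiotics and local inflammation will be treated with topical steroids as necessary".

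Section 17 (Risks to Subjects) says that localized reactions "can be adequately managed and controlled with wound care and topical antibiotics" if a secondary infection develops. Of contact dermatitis after ALA it says: "This can be adequately managed with topical steroids and topical antibiotics, if necessary".

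**The concern.** A subject who reacts to the study drug is a natural candidate for withdrawal under section 16. Once that subject is withdrawn, the section's last sentence, taken at its word, ends data collection of every kind, including the noting of side effects that section 15 calls for. The subjects whose reaction most needs describing would then be those whose record stops.

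What could be lost is descriptive: how the reaction ended, and any side effect reported through the contact number after withdrawal. Sections 12 and 14 say that this treatment has not been investigated before in seborrheic dermatitis, so the outcome of a reaction is useful information even in a pilot of 12 subjects.

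**Working it through.** The plan states no figure on this point, so the check compares the text of the sections.

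**1. Can a reaction lead to withdrawal?**

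- *Directly.* Abnormal sensitivity or allergy to ALA is named in section 16 as a ground. No inference is needed.
- *Through its treatment.* Sections 15 and 17 name drug remedies that can be set against the medication ground in section 16:
  - Secondary infection: antibiotics. If topical, they are another topical medication; if oral or parenteral, they are listed by name.
  - Local inflammation: topical steroids, which are another topical medication.
  - Contact dermatitis: topical steroids and topical antibiotics, which are other topical medications.
  - Wound care is the one named remedy that matches no ground.

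This second route requires reading the medical issues of section 16 to include reactions to PDT. The text permits that reading but does not state it. The direct route stands without it.

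**2. What does the rule stop?**

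- *Before withdrawal:* nothing. The rule concerns further data, so a reaction recognized before withdrawal can already be noted under section 15.
- *After withdrawal, literal reading:* recording of the reaction's later course, and of any side effect reported afterwards.
- *After withdrawal, narrow reading:* only severity grading, swabs and sebum measurements (the data named in section 11) stop, and side effects are still noted.

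Section 16 does not say which reading is meant.

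**3. Does another section settle it?** Section 24 (under the coordinators' role) directs a subject with an adverse effect to the on-call attending, and section 30 provides treatment for injury. Both concern care and not the recording of data. No readable section makes a safety exception to section 16.

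**4. What can be quantified?**

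- Number of subjects affected: not estimable, because no reaction or withdrawal rate is given.
- Weight of one subject in the sample: 1/12 = 8.3%.
- Upper limit on extra recording under the fix: section 10 gives 3 to 4.5 months of participation from enrollment. At 30.44 days per month, 3 × 30.44 / 7 = 13.0 weeks and 4.5 × 30.44 / 7 = 19.6 weeks. If the two-week wait after consent (section 32) falls inside that period, which is an assumption, 11.0 to 17.6 weeks remain from first treatment.

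The last two items describe the study's size and length. They do not measure lost safety data.

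**The case against.** The strongest reply is that this is an ambiguity and not a contradiction. Section 16 speaks of collecting data from the subject, while section 15 speaks of noting side effects, directly after mentioning a number that subjects can call. Staff could stop study assessments and still write down what a withdrawn subject reports. That is a fair reading, and a reader who infers that the two sections flatly contradict each other goes too far: the misfit arises only if section 16 is taken literally. But the literal reading is the one the sentence invites, and nothing in the readable text excludes it.

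It can also be said that the plan promises follow-up to resolution for no one. Section 15 describes monitoring during treatment, and no readable section schedules safety recording at later visits. This stands, and it limits the loss to later spontaneous reports and to what would have been noticed at visits no longer attended. It does not remove the point, because for a withdrawn subject the rule forbids even that.

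Withdrawal is discretionary, and the consent form, Figure 2 and the protocol attachment mentioned in section 10 cannot be seen; any of these might address the matter. Finally, the product is FDA-approved for actinic keratosis and section 34 reports an IND exemption. These considerations argue for low severity, and that is accepted.

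**Conclusion.** The point holds in a limited form. Section 16, read literally, stops the recording of the later course of a reaction that led to withdrawal without consent, and of side effects reported after it. This does not fit section 15. It is a cheap improvement of low severity.

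It rests on the literal reading of section 16 and on the readable text alone. The direct ground, ALA sensitivity or allergy, is enough to support it; the medication ground is an additional possibility that depends on interpretation.

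Several stronger conclusions might be inferred and are not supported:

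- *That the triggering reaction goes unrecorded.* It can be noted before withdrawal takes effect.
- *That safety rates or efficacy results are biased, or care is withheld.* The plan defines no safety rate, and the missing exception bears on neither the efficacy endpoints nor clinical care.
- *That every reaction leads to withdrawal.* All three reactions with a named drug remedy match a ground, but that count leaves out listed risks with no drug remedy of their own, such as pain and photosensitivity, and withdrawal is optional in any case.
- *That pigment change would be lost.* Section 17 lists it as a risk, but it is not itself a ground for withdrawal. It matters here only as a sequel of another reaction, or if reported after withdrawal.

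**What to change.** Replace the last sentence of section 16 with wording such as:

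*No further efficacy, swab or sebum data will be collected after withdrawal. Unless the subject declines, any side effect present at withdrawal or reported afterwards will continue to be noted under section 15, by telephone or at a clinical visit, until it resolves or until the date of the subject's last planned visit, whichever comes first.*

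This makes the narrow reading explicit, respects a subject who wants no more contact, and sets an end date. A side effect still present on that date is noted as unresolved.

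The cost is a one-sentence amendment, matching consent wording, and an occasional telephone contact for the few subjects concerned. Allowing the telephone matters because section 31 leaves travel expense with the subject, to be paid before any compensation arrives. The change does give withdrawn subjects a more explicit follow-up rule than section 15 gives to those who stay; the sponsor may wish to apply the same rule to all subjects.

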## **17) Risks to Subjects**

There is a low chance for any physical, psychological, social or legal injury from participation in the study. The patient will be warned of the standard risks of treatment with topical ALA including erythema, pain, blisters, increased temporary photosensitivity for 24 hours after treatments, and risk for hyper- and hypopigmentation.

These potential adverse events will be localized and can be adequately managed and controlled with wound care and topical antibiotics, if the subject were to develop a secondary infection at the treatment sites. It is also possible, although unlikely, that the subject may develop contact dermatitis after exposure to the topical ALA. This can be adequately managed with topical steroids and topical antibiotics, if necessary.

## **18) Potential Benefits to Subjects**

The individual subject may benefit from the treatment, but this cannot be guaranteed since this study aims to explore the efficacy of PDT in the setting of seborrheic dermatitis. The greater community of patients with seborrheic dermatitis would benefit as this study would provide more insight into the efficacy of PDT for the treatment of seborrheic dermatitis.

PROTOCOL TITLE: Pilot study for the use of photodynamic therapy in the treatment of seborrheic dermatitis

Given that half of the subjects' face will receive the standard PDT treatment, as per the dermatology clinic protocol for actinic keratoses on the face, there is the possibility that the treatments will concurrently treat their actinic keratoses.

**19) Vulnerable Populations**

N/A

**20) Multi-Site Research**

N/A

**21) Community-Based Participatory Research**

N/A

**22) Sharing of Results with Subjects**

N/A

**23) Setting**

The subjects will be recruited from the patients that attend the dermatology clinics at the UC Davis Dermatology clinic.

Research activities will be conducted at the UC Davis Dermatology Department ([name]).

**Coordinators:**

- Role: Patient recruitment, blue light exposure, facial photography, grading of treatment site, specimen collection, data analysis

Seborrheic dermatitis is one of the most common conditions encountered in dermatology and among our patients. Therefore, we will have a sufficient recruitment pool to meet our required number of subjects.

Photodynamic therapy is frequently used at the Dermatology clinic and we do not expect significant adverse effects. However, the patient will be asked to contact the dermatology attending on-call in the event that there is an adverse effect.

To ensure that all assisting personnel are aware of the research protocols, we will have a pre-recruitment meeting followed by regularly scheduled meetings to discuss duty expectations, the protocol, study progress, and any changes as needed.

**25) Prior Approvals**

N/A

**26) Recruitment Methods**

We will recruit from the patients that attend the outpatient dermatology clinic at UC Davis using flyers with contact numbers of the research team. We also use UC Davis Study Pages website. Patients will be assured that their clinical care will not be affected by their participation or non- participation in the study.

Recruitment flyers are attached.

**27) Local Number of Subjects**

A total of 12 subjects will be recruited.

**28) Confidentiality**

This study is not a multicenter study. All of the data will be stored in secured data files in a password-protected computer within a locked room. All of the subjects will be coded with the codes listed in a separate password protected file. All paper files of the subjects will be stored in a locked cabinet within a locked room. [name], [name], and the research coordinator will have access to the paper files and password protected data files.

Subjects' images may be used for educational purposes, publications and/or presentations at conferences, and scientific meetings. Pictures will be used without using any identifying information or features. We will follow the institutional policy for the use of recorded material for educational purposes and/or presentations at

Revision date: November 2, 2018

PROTOCOL TITLE: Pilot study for the use of photodynamic therapy in the treatment of seborrheic dermatitis

conferences, scientific meetings etc... that is outside of the research:

[http://intranet.ucdmc.ucdavis.edu/policies/hospital\\_policies\\_and\\_procedures/consents\\_legal\\_documents/1426.shtml](http://intranet.ucdmc.ucdavis.edu/policies/hospital_policies_and_procedures/consents_legal_documents/1426.shtml)

## **29) Provisions to Protect the Privacy Interests of Subjects**

To protect subjects' privacy interests, data and/or specimens will be labeled with a code that the research team can link to personal identifying information when acquired. The code sheet will be secured and kept separate from the dataset. Only authorized research personnel will have access to this information. All paper records containing study data will be stored in a study binder. This study binder will be securely stored in a locked cabinet, in a locked office, in the UC Davis Department of Dermatology at [name]. Any study-related electronic information will be kept in a password-protected computer database. Only the PI, study staff, IRB and other authorized/designated governing bodies and individuals will be allowed to access these study-related documents. All HIPAA, IRB, State, and Federal policies and guidelines will be followed to ensure patient confidentiality.

Patient photographs taken during this study will be handled according to the UC Davis Dermatology clinic protocol, which is as follows. Photographs will be taken with the clinic's cameras (which never leave the clinic), uploaded to the patient's electronic medical record, and deleted from the camera.

Interviews with patients will be conducted in a private clinic room. The participant may choose not to answer any or all of the questions during the interview, or they may stop the interview at any time, if they are uncomfortable or unsure about the study.

## **30) Compensation for Research-Related Injury**

If the patient is injured as a result of being in the study, the University of California will provide necessary medical treatment. Depending on the circumstances, the costs of the treatment may be covered by the University or may be billed to the patient's insurance company. The University and the study sponsor do not normally provide any other form of compensation for injury.

## **31) Economic Burden to Subjects**

The patient will need to come to the dermatology clinic for the PDT treatments. As such, they will need to pay for the expense of travel. Although this may be offset by compensation for participation in the study, the patient will need to pay for the travel expense ahead of receiving their compensation.

## **32) Consent Process**

Written consent will be obtained from patients at the UC Davis outpatient Dermatology clinic in Sacramento. We will be following the SOP: Informed Consent Process for Research. After obtaining consent, there will be a two-week waiting period before initiating treatment so that the patient may begin using only

PROTOCOL TITLE: Pilot study for the use of photodynamic therapy in the treatment of seborrheic dermatitis

Dove soap and stop using any other products to their face. If the patient is using systemic treatment they will have to wait 4 weeks before participating, and if the patient is using topical treatment they will have to wait 2 weeks before participating. Patient will also be provided a moisturizer and sunscreen to use as needed. Patient will be encouraged to use sunscreen following PDT treatments.

Only English-speaking, adult subjects who are not cognitively impaired and are able to consent will be recruited.

### **33) Process to Document Consent in Writing**

Written documentation of consent process will be obtained (please see attached Consent document). This includes signing of the standardized consent form and HIPPA as well as an additional consent form that outlines permission to use photographs/recording for publications/conferences/training purposes. In combination, this consent process will follow UCDHS policies related to this study and allow use of photographs obtained for conferences/trainings /publications.

### **34) Drugs or Devices**

Aminolevulinic acid (ALA) and the Blu-U unit are routinely used for delivering PDT treatments in the dermatology clinic. The Levulan Kerasticks and Demo Levulan Kerasticks will be at the Investigational Drug Services (IDS), a Division of the Pharmacy Department at the University of California, Davis. IDS dispenses the Kerasticks upon the investigators' request. They will be used as per the UC Davis Department of Dermatology protocol for PDT treatments. PDT is not an investigational drug or device.

Levulan Keastick is approved by the FDA for the treatment of actinic keratosis. The FDA has exempted this protocol from the IND regulations.

